9.1.1 Objective Analysis	21
9.2 SAFETY	21
9.2.1 Safety Parameters.....	21
9.2.2 Safety Analyses.....	21
9.3 MISSING DATA	21
9.4 STATISTICAL METHODOLOGY	21
9.4.1 Data Summary.....	21

9.4.2	Sample Size Justification	22
9.4.3	Interim Analyses	22
9.4.4	Analysis Population	22
10	STUDY MONITORING, AUDITING, AND INSPECTING	22
10.1	STUDY MONITORING PLAN.....	22
10.2	AUDITING AND INSPECTING	23
11	PUBLICATION PLAN	23
12	RISK/BENEFIT ASSESSMENT	24
12.1	RISK CATEGORY, POTENTIAL RISK	24
12.2	EXPECTED COMPLICATIONS AND RATES OF OCCURRENCES	24
12.3	POTENTIAL BENEFITS TO THE SUBJECT	25
13	ETHICAL CONSIDERATIONS	25
14	STUDY FINANCES	26
14.1	FUNDING SOURCE.....	26
14.2	CONFLICT OF INTEREST	26
14.3	SUBJECT STIPENDS OR PAYMENTS	26
15	REFERENCES.....	26

List of Tables

Table 1 Evaluation Schedule	8
Table 2 Simplex HV non-medicated component composition	10
Table 3 Simplex HV Gentamicin component composition.....	11
Table 4 Initial AE report information	17
Table 5 Possible roles of chair and PI	24

List of Figures

Figure 1 Adverse event decision tree.....	15
Figure 2 Component zones	19

List of Appendices

Appendix A Component Listing	28
Appendix B Case Report Forms.....	30
Appendix C 510k Clearance Letters.....	44
Appendix D Instructions for Use	56

List of Abbreviations

ADE	Adverse Device Effect
AE	Adverse Event
BMI	Body Mass Index
CRA	Clinical Research Associate
CRF	Case Report Form
CSM	Clinical Study Manager
DCR	Data Clarification Request
EC	Ethics Committee
HV	High Viscosity
IRB	Institutional Review Board
KSS	Knee Society Score
OKS	Oxford Knee Score
PROMs	Patient Reported Outcome Measures
QoL	Quality of Life
ROM	Range of Motion
SADE	Serious Adverse Device Effect
SAE	Serious Adverse Event
SC	Study Coordinator
TKA	Total Knee Arthroplasty
UADE	Unanticipated Adverse Device Effect

CONFIDENTIAL

This material is the property of Stryker Orthopaedics. Do not disclose or use except as authorized in writing by Stryker.

Study Synopsis

Title	A Retrospective Multicenter Study to Review the Use of Simplex High Viscosity Bone Cement in Primary Total Knee Arthroplasty
Short Title	Simplex HV
Protocol Number	80
Phase	Post Market
Methodology	International, multicenter, retrospective follow-up of a consecutive series of patients
Study Duration	Examination of retrospective patient data from a determined period of 24 months, optional 5 years including pre-operative and intra-operative assessment
Number of Centers	2-5
Objectives	
Primary:
 
To evaluate the success rate of cemented Triathlon Total Knee components implanted using Simplex high viscosity bone cement (Simplex HV). Success is defined as absence of revision due to aseptic loosening in cemented Triathlon Total Knee components implanted with Simplex HV at 24 months.
 
Secondary:
 
To review OKS, KSS results and complications of patients who have received Simplex HV in a Triathlon Total Knee Arthroplasty.

Number of Cases	A minimum of 100 Simplex HV cases and 100 Simplex HV-Gentamicin cases who have received cemented Triathlon Total Knee System will be enrolled.
Inclusion/Exclusion Criteria	
Inclusion Criteria:
 
 A. The Patient is age 18 or over at time of study device implantation B. Patients who have undergone primary Triathlon Total Knee Arthroplasty in which Simplex HV/Simplex HV Gentamicin was indicated for fixation and used on label C. Patients who have been followed for at least 24 months postoperatively 
Exclusion Criteria:
 
 A. Patients who have undergone revision surgery B. Patients who have undergone bilateral Knee Arthroplasty C. Patients contraindicated for either the devices implanted, or the cement used, according to medical history review and instructions for use D. Patient has a cementless tibial baseplate. E. Patient has an active or suspected latent infection in or about the affected knee joint F. Patient has muscle loss or neuromuscular impairment in the affected limb that would create an unjustifiable risk

	
G. Patient is immunologically suppressed or receiving steroids in excess of normal physiological requirements (e.g. > 30 days)
 
H. Patient has a known hypersensitivity to any of the cements constituents or in patients with severe renal failure
 
I. Patient is a prisoner

Study Device	
Bone Cement:
 
• Simplex® HV• Simplex® HV with Gentamicin
Statistical Methodology	
• No sample size calculation because a number of 100 cases per study arm was pre-defined by the regulatory body.• The success rate at two years will be presented with 95% confidence interval.• Frequency and percentage will be presented in tabular form for categorical variables. The mean, standard deviation, minimum and maximum values will be presented for quantitative variables.

Evaluation Schedule

Evaluation	Pre-operative	Intra-operative	24 (+2) months post-operative	27 months up to 5 years post-operative
Inclusion/Exclusion	x			
Demographics & Medical History	x			
KSS	x		x	optional
Surgical Details		x		
Implant and Cement Details		x		
OKS	x		x	optional
A/P and Lateral X-ray Interface			x	optional
Adverse Events		x	x	per protocol

Table 1 Evaluation Schedule

1 Introduction

This document is a protocol for a retrospective human research study. This study will be conducted in compliance with the protocol, international standard ISO 14155 Standards, associated Federal regulations and all applicable research requirements.

1.1 Background

The American Joint Replacement Registry (AJRR) shows an annual increase from approximately 20,000 to almost 130,000 in primary TKAs from 2012 to 2017. In the same time the use of High Viscosity Cement (HVC) in primary knee arthroplasty increased steadily from 46% to 61%¹.

Most of commercially available acrylic bone cements are based upon polymethylmethacrylate (PMMA) and methylmethacrylate (MMA) systems and consist of powdered and liquid components². The polymerization of bone cement occurs through a progression of 4 phases: mixing phase, waiting phase, working phase, and hardening phase. HVC has some advantages over low-viscosity cement (LVC) including shorter mixing and waiting phases, whereas the working and hardening phases are longer. Operational efficiencies are receiving greater interest by surgeons and hospital administrations because high viscosity (HV) bone cements provide a shorter dough time than medium viscosity cements, which may result in surgical efficiencies by

allowing surgeons to handle and apply the cement to implant components and bone earlier while having more time to work with the cement during implantation of the components.^{1,2,3}.

The most common reason for failure of TKA is infection followed by implant loosening, polyethylene wear, and instability⁴. With the use of HVC, the literature describes a focus on aseptic loosening of the tibial component probably resulting from debonding of the cement-tray interface^{3,4}. Considering the exact cause may be unknown, some authors suggest associations of this type of failure to the use of high-viscosity cement^{5,6}. In contrast, a retrospective review of 1851 cases of primary TKA (obese patients with BMI >35) using HVC mixed with Gentamicin showed one revision due to aseptic loosening³.

This study is a retrospective investigation of subjects who have received primary Triathlon Total Knee Arthroplasty inserted with Simplex High Viscosity (HV) Cement to evaluate the success rate defined as absence of revision for aseptic loosening of components at two years postoperative.

1.2 Clinical Data to Date

This study is the first Stryker Joint Replacement sponsored retrospective data collection on the Simplex HV bone cement.

2 Clinical Study Plan

2.1 Study Design

A retrospective, post-market, multi-center design will be employed.

2.2 Study Centers

Cases will be enrolled retrospectively at two to five centers which will enroll a minimum of 100 cases with Simplex HV non-medicated and 100 cases with Simplex HV with Gentamicin. All participating centers will comply with the federal regulations and apply at the responsible Institutional Review Board (IRB) or Ethics Committee (EC) for patient informed consent waiver. Non-compliance of a study center may result in termination of the center's participation in the study.

2.3 Number of Subjects

Cases will be enrolled until a total of 100 cases with Simplex HV non-medicated and 100 cases with Simplex HV with Gentamicin were observed and collected. Depending on the hospital

standard of care, a site may only enroll subjects receiving Simplex HV non-medicated and another site may only enroll subjects receiving Simplex HV with Gentamicin.

3 Device Description

3.1 Study Device

Simplex HV is available non-medicated and medicated with Gentamicin antibiotic.

The US listing number are Simplex HV: D295829 and Simplex HV with Gentamicin: D295830.

The Simplex HV bone cement is FDA recognized and registered under D-U-N-S-Number 344261631¹.

Simplex HV with Gentamicin is registered in the Australian Register of Therapeutic Goods (ARTG) under 276417.

Simplex HV/Gentamicin is CE certified under 135-0581-01 and Simplex HV under 135-0595-01.

3.1.1 Simplex HV Non-medicated Orthopaedic Cement

Simplex HV bone cement is a fast-setting acrylic resin for use in bone surgery. Mixing the two separate sterile components produces a ductile bone cement which, after hardening, fixes the implant and transfers stresses produced during movement evenly to the bone. Simplex HV cement powder also contains insoluble zirconium dioxide as an X-ray contrast medium. Simplex HV does not emit a signal and does not pose a safety risk in a magnetic resonance environment. Simplex HV is a substance designed to be used in arthroplastic and/or osteosynthetic procedures for the fixation of polymer or metallic implants to the living bone. It is typically made from methylmethacrylate, polymethylmethacrylate (PMMA)², esters of methacrylic acid or copolymers containing polymethylmethacrylate and polystyrene. This device does not contain an antimicrobial agent. The option for high viscosity does not compromise depth of intrusion. After application, this device cannot be reused.

Composition of cement powder:	40g	Composition of liquid:	20ml
Poly (methylacrylate/methylmethacrylate)	33.7 g	Methylmethacrylate (stabilized with 60 ppm HQ)	18.4 g
Zirconium dioxide	6 g	N,N-dimethyl-p-toluidine	0.4 g
Benzoyl peroxide	0.3 g		

Table 2 Simplex HV non-medicated component composition

¹The FDA formally recognized the D-U-N-S-Number as an acceptable unique facility identifier (UFI) for the Foreign Supplier Verification Programs (FSVP). The identification of importers will help the FDA effectively implement, monitor compliance with, and enforce the FSVP requirements.

²Simplex HV bone cement contains 40g polymethyl methacrylate (PMMA) powder and 20 ml methylmethacrylate (MMA) liquid.

In partial or total replacement of the hip, knee and other joints, Simplex HV is indicated for fixation of synthetic resin polymer and metal prosthesis components in uninfected vital bones if joint reconstruction is required. In tumour surgery, Simplex HV is used in combination with internal fixation to fill bone cavities after tumour removal.

The use of Simplex HV is contraindicated if muscle wasting or neuromuscular compromise in the affected limb renders the procedure unjustifiable. Simplex HV should not be used in the event of known hypersensitivity to any of its constituents or if there are active or inadequately treated infections in the region of the implant.

3.1.2 Simplex HV with Gentamicin

Simplex HV bone cement with Gentamicin is a fast-setting acrylic resin with addition of Gentamicin sulfate for use in bone surgery. The added antibiotic, Gentamicin sulfate, protects the implant and the surrounding tissue from colonization with pathogens that are sensitive to gentamicin. Simplex HV with Gentamicin cement powder also contains insoluble zirconiumdioxide as an X-ray contrast medium. Simplex HV with Gentamicin does not emit a signal and does not pose a safety risk in a magnetic resonance environment.

Mixing the two separate sterile components produces a ductile bone cement which after hardening, fixes the implant and transfers stresses produced during movement evenly to the bone.

Composition of cement powder:	40.8 g	Composition of liquid:	20ml
Poly (methylacrylate/methylmethacrylate)	33.7 g	Methylmethacrylate (stabilized with 60 ppm HQ)	18.4 g
Zirconium dioxide	6 g	N,N-dimethyl-p-toluidine	0.4 g
Benzoyl peroxide	0.3 g		
Gentamicin base (added as Gentamicin sulfate)	0.5 g (0.8 g)		

Table 3 Simplex HV Gentamicin component composition

Simplex HV with Gentamicin is indicated for fixation of synthetic resin and metal prosthesis components during partial or total replacement of the hip and knee as well as other joints, if an infection with organisms that are sensitive to gentamicin is diagnosed or suspected. The antibiotic provides protection against bacterial colonization of the implant and the surrounding tissue.

Simplex HV with Gentamicin can be used for filling and stabilizing bone defects within the scope of internal fixation treatment, if there is an increased risk of infection with pathogens that are sensitive to gentamicin.

The use of Simplex HV with Gentamicin is contraindicated, if muscle wasting or neuromuscular

compromise in the affected limb renders the procedure unjustifiable. Simplex HV with Gentamicin should not be used in the event of known hypersensitivity to any of its constituents or in patients with severe renal failure.

3.2 Ancillary Devices

Additionally, only the following **Stryker Orthopaedics compatible** ancillary devices may be used, according to this study protocol:

- Triathlon Total Knee System

4 Study Procedures

4.1 Subject Recruitment and Screening

Subjects will be enrolled at the study centers using the electronic medical record, paper charts, information from pre- and postoperative images, intraoperative notes, and follow-up data collected as part of the hospital's routine care. The eligibility of these subjects will be assessed, according to the inclusion/ exclusion criteria.

All personal identifiable patient information will be pseudonymized and tracked via a unique subject number, known only to the site. Data extracted from the subject hospital files (paper or electronically stored); will be entered into paper case report forms (CRF).

4.2 Patient Informed Consent and Guidelines

The study protocol will be submitted for IRB/ EC Review. As pseudonymized retrospective patient data will be used, a requirement for informed consent is not expected, however waiver of consent from the IRB/EC is required.

5 Study Details

5.1 Inclusion/Exclusion Criteria

Inclusion Criteria:

- A. The Patient is age 18 or over at time of study device implantation
- B. Patients who have undergone primary Triathlon Total Knee Arthroplasty in which Simplex HV/Simplex HV Gentamicin was indicated for fixation and used on label
- C. Patients who have been followed for at least 24 months postoperatively

Exclusion Criteria:

- A. Patients who have undergone revision surgery
- B. Patients who have undergone bilateral Knee Arthroplasty
- C. Patients contraindicated for either the devices implanted, or the cement used, according to medical history review and instructions for use
- D. Patient has a cementless tibial baseplate.
- E. Patient has an active or suspected latent infection in or about the affected knee joint
- F. Patient has muscle loss or neuromuscular impairment in the affected limb that would create an unjustifiable risk
- G. Patient is immunologically suppressed or receiving steroids in excess of normal physiological requirements (e.g. > 30 days)
- H. Patient has a known hypersensitivity to any of the cements constituents or in patients with severe renal failure
- I. Patient is a prisoner

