8.5 Protocol Deviations

Any major deviation from this protocol will be recorded and must be reported to the EC/IRB by the investigational site according to their reporting procedures. Major protocol deviations for this study may include the following; this list may not be all-inclusive:

- Patient enrolled does not meet the inclusion/exclusion criteria
- Protocol specified study component(s) not implanted

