9.1 Study Objectives

9.1.1 Objective Analysis

To evaluate the success rate of cemented Triathlon Total Knee components implanted using Simplex high viscosity bone cement (Simplex HV). Success is defined as absence of revision of cemented Triathlon Total Knee components implanted with Simplex HV for aseptic loosening at two years postoperative. 95% confidence interval of the success rate will be presented as well.

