9.4 Statistical Methodology

9.4.1 Data Summary

Descriptive statistics will be computed for all baseline conditions and demographic parameters. That is, for continuous data, the N, mean, median, standard deviation, minimum and maximum will be computed. For categorical data, the frequency will be computed. The data will be presented by appropriate subgroups (e.g., center, gender).

A Kaplan-Meier survivorship curve will be displayed for revision and/or removal of the Triathlon total knee arthroplasty cemented with Simplex HV for aseptic loosening.

A Kaplan-Meier survivorship curve will be displayed for all-cause revision and/or removal of the Triathlon total knee arthroplasty cemented with Simplex HV with Gentamicin for aseptic loosening.

Two year Kaplan-Meier success rate with 95% CI will be presented.

For all additional data collected that are not required for direct support of a study objective, data will be summarized according to follow-up. For parameters represented by continuous variables (e.g., ROM), the summaries will consist of the N, mean, median, standard deviation, minimum, and maximum values.

Documentation of statistical analyses utilizing SAS® software version 9.3 or higher will be maintained.

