9.4.4 Analysis Population

Per Protocol Population: The study population will include all non-censored subjects who have received the Triathlon total knee system cemented with Simplex HV and are available for objective analysis.

The objective analyses will be based on the per protocol population.

Safety Population: The safety population will include all non-censored subjects who received the Triathlon total knee system cemented with Simplex HV.

The safety analysis will be based on the safety population.

10 Study Monitoring, Auditing, and Inspecting

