Appendix B Case Report Forms

Title page

Simplex HV Bone Cement

A Retrospective Multicenter Study to Review the
Use of Simplex High Viscosity Bone Cement
in Primary Total Knee Arthroplasty

[figure not shown]
stryker®

Study # 80

Patient code (Use AA, BB,...AB)	

		

			Patient ID	

8	0	

Study #		

	8	0	Study #		

			

Center#			

				Center#			

			

Subject #			

				Subject #			

		

Side (L/R)		

			Side (L/R)	
8	0																											
Study #																												
Center#																												
Subject #																												
Side (L/R)																												

Stryker®		Simplex HV Retrospective Study					
Page 1 of 1		INCLUSION / EXCLUSION			Patient ID		
		8 0		Study#	Center#	Subject#	Side (L/R)
GENERAL INFORMATION							
Patient code (Use AA, BB,...AB)				Date of examination		 D D M M M Y Y Y Y	
I. INCLUSION CRITERIA							
Yes No							

A.   The patient is aged 18 years and over at time of study device implantation.
 
B.   Patients who have undergone primary Triathlon Total Knee Arthroplasty in which Simplex HV/ Simplex HV Gentamicin was indicated for fixation and used on label.
 
C.   Patients who have been followed for at least 24 months postoperatively
							
All of the above must be answered "Yes" for the patient to be enrolled in the study.							
II. EXCLUSION CRITERIA							
Yes No							

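### Inclusion C admits only patients followed to 24 months, so no earlier death can reach the safety table and the 2-year rate covers only those patients; an undefined non-censored filter separately narrows both analysis populations

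*Combined protocol and SAP*

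**What the plan says.** Inclusion C, in the synopsis, Section 5.1 and the eligibility form, admits "Patients who have been followed for at least 24 months postoperatively". The form is strict: "All of the above must be answered 'Yes' for the patient to be enrolled in the study". Section 8.5 gives as an example of a major deviation "Patient enrolled does not meet the inclusion/exclusion criteria". Section 2.3 sets the stopping rule: "Cases will be enrolled until a total of 100 cases with Simplex HV non-medicated", and the same number with gentamicin.

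Other parts of the plan point to a wider population. The synopsis describes follow-up of consecutive patients. Section 9.1.1 states the objective for components implanted with the cement, not for patients still under follow-up. Section 6.1 starts adverse event reporting at surgery, Section 6.2 puts death first among the serious criteria, and Section 12.2 names sudden death among the known complications.

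On analysis, Section 9.4.1 says: "Two year Kaplan-Meier success rate with 95% CI will be presented". Section 9.4.4 defines the per protocol population as follows: "The study population will include all non-censored subjects who have received the Triathlon total knee system". For safety it says: "The safety population will include all non-censored subjects who received the Triathlon total knee system cemented with Simplex HV". The word non-censored is not defined in the text supplied. Section 9.2.1 counts revision and removal rates among the safety parameters.

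**The concern.** There are two separate problems.

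The first is entry. Inclusion C depends on what happened after surgery. Because enrolment runs to a fixed count, a patient who died or was lost early is in effect replaced by one who was not. Section 9 plans no count of those left out, so the report would show no early deaths and a 2-year rate with almost no censoring, and nothing in it would show that both follow from the entry rule. A Kaplan-Meier rate normally signals that incomplete follow-up was handled in the analysis; here it would have been removed beforehand.

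The second is the filter in Section 9.4.4. A survival analysis needs its censored subjects, and a safety population should not depend on censoring status. Depending on what the word means, the filter either repeats Inclusion C or removes knees that had a revision the safety section promises to count.

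**Working it through.** **1. Who can enter under Inclusion C**

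- Death at month 3: fails Inclusion C, is not enrolled and cannot be tabulated.
- Lost at month 10: the same.
- Non-fatal early embolism, followed to 24 months: enrolled, and reportable from surgery (Section 6.1).
- Death after 24 months, within the reporting period: enrolled and reportable.
- Knee revised at month 12, patient followed to 24 months: meets Inclusion C; entry then depends on how Exclusion A (patients with revision surgery, no timing stated) is read.

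The count of deaths before 24 months is therefore 0 whatever happened. The documents give no mortality figure. At an assumed 24-month risk p of 0.5%, 1% or 2%, 100 consecutive implantations would contain at least one death with probability 1 − (1 − p)^100 = 39%, 63% or 87%.

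**2. What the 2-year rate estimates**

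If everyone is followed to 24 months, Kaplan-Meier equals the crude proportion. With 2 failures in 100: (99/100) × (98/99) = 0.98 = 98/100. If k other-cause revisions are censored before both failures, it is (98 − k)/(100 − k): 97.98% for k = 1 and 97.89% for k = 5. The difference from crude is at most 0.11 point.

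Let L be the share of implanted cases not followed to 24 months, S1 the success rate in those followed and S0 the rate in those not followed. The rate over all implanted cases is (1 − L) × S1 + L × S0, so the reported S1 differs from it by L × (S1 − S0). The documents give neither L nor S0, and the plan would collect neither. The difference is zero if S1 = S0, that is, if loss is independent of revision.

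**3. What the non-censored filter could do**

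If it means not lost before 24 months, it adds nothing to Inclusion C. If it means not censored on the aseptic-loosening curve before 24 months, the usual convention drops knees revised for another cause.

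Assumptions for the second reading: 100 enrolled knees, 2 aseptic revisions, k other-cause revisions, and revised knees enrollable (Exclusion A not read as covering revision of the index knee).

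| k | All-cause success, all cases: 1 − (2 + k)/100 | After the filter: 1 − 2/(100 − k) | Difference (points) |
|---|---|---|---|
| 1 | 97.00% | 97.98% | +0.98 |
| 3 | 95.00% | 97.94% | +2.94 |
| 5 | 93.00% | 97.89% | +4.89 |

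For the primary aseptic-loosening rate, the crude value on all cases is 98.00%. After the filter it is 97.98% to 97.89%, a shift of at most 0.11 point.

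**The case against.** Series with a minimum follow-up are common and can be valid; the title of one of the protocol's own references announces a 2-year minimum. The 24-month requirement is stated openly in the synopsis, in Section 5.1 and on the form. Section 12.2 lists embolism and infarction as complications, not as deaths, and non-fatal cases in followed patients remain reportable. By the figures above, the primary rate hardly moves under the filter. All of this stands, and it limits the point to one of scope and reporting. It does not explain why the plan claims a consecutive series and an objective for implanted components while leaving out the counts that would connect them to the enrolled cases.

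The filter illustration also depends on Exclusion A. Read literally, Exclusion A removes every revised knee, and the filter then has no other-cause revisions left to drop. That objection is correct. The table therefore states the assumption, and the fix deals with Exclusion A.

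The follow-up forms offer a visit box starting at 12 months, which conflicts with the 24-month visit in the evaluation schedule. It should be reconciled, but it does not waive Inclusion C.

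**Conclusion.** The point holds on the text. No death before 24 months can reach the safety table, and the 2-year success rate describes only patients followed to 24 months. Neither statement needs an assumption about event rates. Separately, the non-censored restriction is undefined. Under a plausible reading it would take other-cause revisions out of the safety population, overstating all-cause success by 0.98 to 4.89 points at the assumed counts and with revised knees enrollable.

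Four stronger readings are not supported:

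- A reader might infer that the success rate is inflated. The documents give no loss rate and no outcome for unfollowed patients, so direction and size are unknown.
- A reader might infer that all early serious events are lost. Only those in patients who died or were lost before 24 months are.
- A reader might put a confidence interval on the zero deaths. The plan tabulates frequency and percentage of adverse events and calculates no such interval.
- Taken literally, the filter would drop every event-free knee. Nothing suggests that this is meant.

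The point should be fixed, at the low end of that grade: the effect on early deaths is certain, but the shown effect on the primary rate is small.

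**What to change.** 1. **Section 9.4.4.** Delete non-censored from both definitions. Base safety on all enrolled cases that received the device. State that the aseptic-loosening curve is censored at the last date of known implant status.
2. **Synopsis, Section 5.1 and eligibility form.** State that Exclusion A refers to revision before the index surgery. This is needed under either option below.
3. **Preferred option for Inclusion C.** Replace it with *index surgery at least 24 months before the data cut-off*, state the cut-off date, and enrol the consecutive series that the synopsis describes. Report per arm the numbers screened, died, lost, and with known implant status at 24 months.
4. **Minimum option if eligibility must stay.** Keep Inclusion C. Report per arm, from the eligibility screening, the numbers screened, died and lost before 24 months, with cause of death where the chart gives it. State beside each result that the success rate and safety table apply only to patients with 24 months or more of follow-up.

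Either option needs a protocol amendment with EC/IRB approval (Section 13) and a screening tally. The preferred option also needs a last-contact date, gives a smaller N for the 24-month OKS, KSS and X-ray, and may bring informative censoring at last contact. If the regulator's 100 per arm (Section 9.4.2) means completed cases, an assumed 10% to 30% attrition requires 100/0.9 = 111.1 to 100/0.7 = 142.9, so 112 to 143 implantations per arm.

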
A.   Patients who have undergone revision surgery
 
B.   Patients who have undergone bilateral Knee Arthroplasty
 
C.   Patients contraindicated for either the devices implanted, or the cement used, according to medical history review and instructions for use.
 
D.   Patient has a cementless tibial baseplate.
 
E.   Patient has an active or suspected latent infection in or about the affected knee joint
 
F.   Patient has muscle loss or neuromuscular impairment in the affected limb that would create an unjustifiable risk.
 
G.   Patient is immunologically suppressed or receiving steroids in excess of normal physiological requirements (e.g. > 30 days)
 
H.   Patient has a known hypersensitivity to any of the cements constituents or in patients with severe renal failure
 
I.   Patient is a prisoner.
							
All of the above must be answered "No" for the patient to be enrolled in the study.							
III. Comments							

							
Investigator Name (Print)				For Stryker Use Only		INITIAL/DATE:	
Investigator Signature				Stamp Date Received:		Monitored: /	
Date		 D D M M M Y Y Y Y				Receipt: /	
						Entry: /	
						Verification: /	

Stryker® Simplex HV Retrospective Study												
Page 1 of 1			PRE-OP / DEMOGRAPHICS			Patient ID			8 0			
									Study#	Cont#	Subject#	Side (L/R)
GENERAL INFORMATION												
Patient code (Use AA, BB,...AB)						Date of examination						
									D D	M M M	Y Y Y Y	
DEMOGRAPHICS												
Age		Height		Weight		BMI		Gender				
								 male	 female			
DIAGNOSIS												
Patient's Initial Diagnosis						Operative side						
 Osteoarthritis			 Post Traumatic Arthritis			 left			 right			
PREOPERATIVE MEDICAL HISTORY (Relevant concurrent medical condition and treatment)												
Specify disease						Specify treatment						

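### Exclusion A has no time anchor: applied literally to charts with 24 months of follow-up it would screen out every primary-endpoint failure, though a baseline meaning is likely

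*Combined protocol and SAP*

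**What the plan says.** Exclusion A in Section 5.1 reads "Patients who have undergone revision surgery". The Study Synopsis and the Inclusion/Exclusion form in Appendix B carry the same words. None of the three names a date, a knee or a reference operation. By contrast, Inclusion A ties age to the time of implantation.

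Eligibility is assessed from existing records, which under Section 4.1 include "intraoperative notes, and follow-up data collected as part of the" hospital's routine care. Inclusion C then requires "Patients who have been followed for at least 24 months postoperatively". The enrolment form closes its exclusion list with "All of the above must be answered 'No' for the patient to be enrolled in the study". Section 8.5 names as a major deviation, reportable to the EC/IRB: "Patient enrolled does not meet the inclusion/exclusion criteria".

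The primary endpoint is in Section 9.1.1: "Success is defined as absence of revision of cemented Triathlon Total Knee components implanted with Simplex HV for aseptic loosening at two years postoperative".

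**The concern.** In a retrospective study the outcome is already in the chart when eligibility is decided. An undated exclusion for revision surgery can therefore be answered from the outcome itself. An abstractor who works from the enrolment form and finds a knee revised at, say, month 14 has a plain yes on item A. The form says not to enrol, and the deviation rule discourages enrolling anyway.

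If that happens, failures disappear before analysis. Section 2.3 continues enrolment until 100 cases per cement are collected, so a rejected failure would simply be replaced. The documents describe no log of rejected charts. A reader of the results could not then tell a true 100% from one produced by the eligibility rule, and the study could not inform the question in Section 1.1 about high-viscosity cement and loosening.

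**Working it through.** **Step 1. Does the literal reading remove every failure?** A primary failure is, by definition, a revision (Section 9.1.1). Every failure therefore satisfies item A at chart review. The radiographic definition of loosening in Section 7.1 is not part of the success definition, so it offers no other way for a failure to be enrolled and counted. Failures possible among enrolled knees: 0, at any true rate.

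**Step 2. Inputs.**
- Cases per cement: 100 (Sections 2.3 and 9.4.2). Section 9.4.2 says no sample size calculation was made, so there is no planned figure to reproduce.
- Interval: 95%, method not named for the success proportion (Section 9.1.1). The exact Clopper-Pearson interval is assumed here.
- Only loosening count in the documents: 1 revision in 1851 cases, in obese patients with gentamicin high-viscosity cement (Section 1.1).
- Other failure rates below are assumptions.

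**Step 3. What the literal reading would report.** For 100 successes in 100, the exact lower limit is 0.025^(1/100) = 0.9638, so the interval is 96.4% to 100%. It excludes the truth when the true failure rate p exceeds 1 − 0.9638 = 0.0362, or 3.6%. If both cements were pooled, 200 in 200 would give 98.17% to 100%, and the threshold would be 1 − 0.9817 = 1.8%.

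The reported rate is 100% and the true rate is 100% − p, so the point estimate is too high by exactly p.

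**Step 4. How much would differ from an unselected series?** If revised knees are kept, the chance that 100 cases show no failure anyway is (1 − p)^100. The exact 95% interval for 1/1851 = 0.054% runs from 0.0014% to 0.30%.

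| True failure rate p | Source | Upward bias (points) | Chance of 0/100 if revised knees are kept | Does 96.4–100% cover the truth? |
|---|---|---|---|---|
| 0.054% | 1/1851 | 0.054 | 95% | yes |
| 0.30% | upper limit of 1/1851 | 0.30 | 74% | yes |
| 1% | assumed | 1 | 37% | yes |
| 2% | assumed | 2 | 13% | yes |
| 3% | assumed | 3 | 5% | yes |
| 5% | assumed | 5 | 0.6% | no |

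**The case against.** The strongest reply is that the context supplies the missing date, and much of it does point that way:

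- The row for eligibility in "Table 1 Evaluation Schedule" is ticked in the pre-operative column only.
- Section 6.1 treats abnormalities found at screening as pre-existing, and new findings from surgery forward as adverse events. A later revision falls on the second side.
- Section 6.3 asks for 24-hour reporting of certain reoperations of the study knee, so reoperated knees are expected among enrolled patients.
- Exclusion B, on bilateral arthroplasty, is just as undated, yet item 5 of the Follow-up form has a dated field for contralateral knee replacement after the study surgery.
- Exclusion E, "Patient has an active or suspected latent infection in or about the affected knee joint", is also undated, while Section 12.2 lists wound infection among the findings to be expected.
- The synopsis describes a consecutive series.
- Revision rates (Section 9.2.1), Kaplan-Meier curves (Section 9.4.1), and the loosening and revision-date fields on the Follow-up and Adverse Event forms would have little purpose if revised knees were barred.

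Most of this stands: it makes a baseline meaning the likely intention. It does not tell an abstractor how to answer item A. Table 1 cannot settle the matter, because Inclusion C sits on the same checklist and cannot be judged pre-operatively. Read as a bar on index operations that were themselves revisions, item A largely repeats the requirement for a primary arthroplasty in Inclusion B. It also shares its verb form with Inclusion B, which describes status at chart review.

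A second objection is that the arithmetic is mild, and this holds within limits. Near 1/1851 the two readings would usually give the same result. A reader might infer from the 37% at 1% that the interval becomes misleading from about there. It does not: for 100 cases it still covers the truth up to 3.6%. Nor should a zero-width Greenwood interval be charged to Exclusion A, since any series without events produces one.

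**Conclusion.** The point holds in conditional form. Followed as written, Exclusion A removes every primary-endpoint failure and fixes the success rate at 100%. Intended meaning and written rule probably differ, and no section closes the gap.

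A reader might go further and infer that failures were in fact excluded, or that the design was meant to exclude them. The documents do not support either. No section shows a site applying the literal reading, and the planned revision analyses and form fields argue against that intent.

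If the literal reading were applied, the point estimate would be too high by the true two-year failure rate. With 100 cases and an exact interval, the truth would be missed only above 3.6%. At the single cited count the effect is negligible. That count comes from obese patients with gentamicin cement, while Section 1.2 calls this the sponsor's first retrospective data collection on Simplex HV, so it cannot be assumed to carry over. The higher rates in the table are assumptions, not evidence that the effect is large. The case for correcting the text is that the ambiguity bears on the primary endpoint, its effect would be invisible in the results, and the repair is small.

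**What to change.** In the Study Synopsis, Section 5.1 and the Appendix B enrolment form, limit Exclusion A to revision surgery before or at the index operation. Add one sentence: revision or removal of the study knee after the index surgery is a study outcome and never a reason for exclusion.

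A related but separate point is Inclusion C. State that a knee revised before 24 months satisfies it as followed to its event. Otherwise early failures could still be screened out there after Exclusion A is corrected.

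Re-screen any chart known to have been rejected on item A for a revision after the index surgery. If such rejections were not recorded, say so in the report.

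The cost is a short protocol and form amendment submitted to the EC/IRB (Section 13) at two to five centers (Section 2.2). Re-screening may not be possible everywhere. The success rate may come out slightly less favourable. If the baseline meaning was intended all along, nothing in the design changes.
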